**Figure 1. Example of Treatment Period and T-VEC Monotherapy Period**

- Treatment-Emergent Adverse Events

Treatment-emergent adverse events are events occurring during the Treatment Period. Adverse events occurring on the same day of the start or end day of the treatment period will be counted as treatment-emergent adverse event unless there is evidence to indicate otherwise (eg, the checkbox in CRF, which indicates a AE

onset is prior to first dose of talimogene laherparepvec or surgical resection, is checked).

- Treatment Emergent Death

Treatment emergent death is defined as any death that occurs during the treatment period. Any treatment emergent death will be reported as an SAE.

- Safety Follow-Up

Safety follow-up will be performed approximately 30 (+ 15) days after the last dose of talimogene laherparepvec or the completion of the surgical resection of melanoma tumor lesion(s), whichever is later.

- End of Study

Primary Completion: the time when the last subject is assessed or receives an intervention for the purposes of final collection of data for the primary analysis. The primary completion is anticipated to occur at the later time of either the occurrence of approximately 64 events (local, regional or distant recurrence of melanoma or death) or approximately 2 years after the end of randomization.

End of Trial: the time when the last subject is assessed or receives an intervention for evaluation in the study. The end of trial will occur when the last subject has had the opportunity to complete the long-term follow-up. The end of trial is anticipated to occur approximately 5 years after the end of randomization.

- Long-term Follow-up

Long-term Follow-up will occur every 3 months ( $\pm$  30 days) for 3 years following the safety follow-up visit and then every 6 months ( $\pm$  30 days) until death, subject withdraws full consent, or up to 5 years after the last subject is randomized, whichever is first.

- Concomitant Medications

The concomitant medications include all non-anticancer medication during treatment period.

- On-treatment Procedure/Surgery

The on-treatment surgery includes all surgery subjects receive during treatment period except the protocol specified surgical resection of melanoma lesion(s)

- Prior Systemic Anti-cancer Therapies

Prior systemic anti-cancer therapies for melanoma include chemotherapy, chemoradiotherapy, immunotherapy, targeted biologics, targeted small molecules, and chemo-embolization which are not in the setting for adjuvant or neoadjuvant treatment.

- Previous Systemic Immune Check-Point Inhibitor Therapy for Melanoma

Previous systemic immune check-point inhibitor anti-cancer therapies (eg, anti-CTLA4, anti-PD1) not in the setting for adjuvant or neoadjuvant treatment.

- Subsequent Anti-Cancer Therapy for Melanoma after Recurrence

Subsequent anti-cancer therapy for melanoma is defined as any anti-cancer therapy (or treatment) received for melanoma after recurrence. Subsequent anti-cancer therapy for melanoma will be collected from CRF form “Subsequent Anti-Cancer Therapies for Current Malignancy”.

- Adjuvant therapy for Melanoma

Adjuvant therapy is defined as anti-cancer therapy subjects receive after surgical resection of melanoma lesion(s) but before recurrence. Adjuvant therapy will be collected from CRF form “Subsequent Anti-Cancer Therapies for Current Malignancy”.

- Landmark OS by year

Estimated proportion of subjects alive at each year by the Kaplan-Meier method.

- Landmark RFS by year

Estimated proportion of subjects experiencing overall recurrence (local, regional, distant) at each year by the Kaplan-Meier method.

- Response (Arm 1 only)

Refer to [Section 4.1.2.1.1](#).

- Best overall response (BOR) per investigator (Arm 1 only)

Best response for a subject is the best overall response observed across all time points in the following order: CR, PR, SD, PD or UE.

- Histopathology Tumor-free margin (R0) Surgical Resection Rate

Histopathology tumor-free margin (R0) surgical resection is defined by pathologist as absence of ink on the tumor for all disease. R0 surgical resection rate is defined as proportion of subjects with R0 resection. For each subject, the R0 resection status (R0 or non-R0) will be derived from lesion level resection status collected from CRF. In order for a subject to count as an R0 resection event, all lesion observations will be R0 within the given subject. Any observation of a non-R0 (R1, R2) for a subject will make the subject a non-R0 case for this endpoint.

- Pathological Complete Response (pCR) Rate (Arm 1 Only)

Pathological Complete Response (pCR) is defined as no evidence of viable tumor cells on complete pathological evaluation of the surgical specimen per institutional standards of care. pCR rate is defined as proportion of subjects which achieves a pCR. For each subject, the pCR status (pCR or non-pCR) will be determined based on whether or not viable tumor was detected in the surgical specimen.

- Last Valid Tumor Evaluation

For overall tumor response per modified WHO response criteria the last valid tumor evaluation refers to the last valid tumor response assessment (PR, CR, SD or PD) per investigator. For the subject-level tumor response based on the tumor burden of a subset of lesions (injected, uninjected lesions, or other subtype) or the lesion-level response the last valid tumor evaluation refers to the assessment where the corresponding tumor burden or the corresponding individual tumor area is not missing.

- Baseline Lesion

Lesions measured at the most recent visit on or before receiving the first administration of talimogene laherparepvec (i.e., study day 1) will be flagged as baseline lesions. Baseline lesions must have positive tumor area. Lesions reported in the baseline measurable lesion CRF page but with a tumor area of zero or missing value at the last measurement on or before study day 1 will not be considered baseline lesions.

- New Lesion

New lesions are those that first appear after study day 1 with a positive tumor area or lesions without a positive lesion area in the last assessment on or before study day 1

but a positive lesion area from follow up tumor measurements. Baseline tumor area of a new lesion is obtained from the earliest date with positive bi-dimensional tumor measurements after study day 1. If a new lesion(s) that appears in between scheduled tumor response assessments disappear(s) before the next scheduled assessment, there is no need to include this lesion for tumor response evaluation

- Evaluable Lesion

A baseline or new measurable lesion is defined as evaluable if it has an initial positive area followed by at least 1 assessment with a non-missing area.

- Injected/Uninjected Lesion

Baseline or new lesions that are reported as injected with talimogene laherparepvec at any time during the treatment period are considered injected lesions. Baseline or new lesions that are not reported as injected with talimogene laherparepvec are considered uninjected lesions.

- Baseline Tumor Burden

The baseline tumor burden for a subject is the sum of the initial area of baseline lesions of the specific lesion type.

- Tumor Burden

The tumor burden for a subject at a visit is the sum of the area at that visit of baseline lesions of the specific lesion type.

- Evaluable Tumor Burden

A subject is defined as having an evaluable tumor burden of a specific type (injected, uninjected) if they have at least one evaluable tumor burden assessment of the specific type. An evaluable assessment is one with a tumor burden that includes all lesions of the specific type with a non-missing area that were included in a baseline tumor burden assessment.

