When an non-index lesion splits into two or more lesions, the apparently larger lesion will be reported as a non-index lesion. All other smaller lesions will be reported as new non-index lesions with an indication that the lesion split from the specified lesion. In this case, appearance of a new lesion from a previous lesion that split will not be considered

disease progression solely due to appearance of a new lesion (may be considered disease progression due to > 25% increase in the sum of the products of the perpendicular diameters of all index tumors since baseline, or the unequivocal appearance of a new tumor, other than the product of the split tumor, since the last response assessment time point).

Measureable Tumor Assessment/Burden:

Baseline Documentation of “Index Lesions”:

All baseline evaluations should be performed as close as possible to randomization and never more than 4 weeks (ie, 28 days) prior to randomization.

At baseline, up to 10 measurable cutaneous, nodal, or soft tissue lesions will be chosen to measure over the course of therapy. The distribution of these index lesions should be representative of the subject’s overall disease status. Index lesions should be selected on the basis of their size (lesions with longest bi-dimensionally perpendicular diameters) and suitability for accurate repeated measurements by imaging techniques (CT, MRI or ultrasound) and/or other method such as clinical exam.

The sum of the products of the largest perpendicular diameters of all index lesions will be calculated and reported.

If a subject has multiple small superficial cutaneous melanoma lesions at baseline (each lesions is less than 10 mm in at least 2 dimensions) which in aggregate have a total diameter of ≥ 10 mm in at least 2 dimensions, up to 10 largest lesions that were included in this measurement will be reported as “Index Lesions”, and the sum of the products of the two largest perpendicular diameters of these lesions will be calculated and reported for tumor response assessments.

Baseline Documentation of “Nonindex Lesions”:

All other lesions (or sites of disease), including any measurable lesions that were not chosen as index lesions will be identified as nonindex lesions. Nonindex lesions should be recorded and assessed qualitatively over the course of therapy.

Follow-up “Index Lesions”:

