#### **4.1.2 Secondary Endpoint**

##### **4.1.2.1 Efficacy Endpoints**

##### **4.1.2.1.1 Tumor Response (Arm 1 Only)**

The overall tumor response is evaluated up to the earlier of surgical resection or subsequent anti-cancer therapy. Lesion-level response is evaluated up to the earliest event of start of subsequent anti-cancer therapy, merge with another lesion, or resection. Subject-level response is evaluated up to the earliest event of start of subsequent anti-cancer therapy or a partial or complete lesion resection.

Following endpoints will be analyzed for tumor response analysis,

- The overall tumor response is per the modified WHO criteria of tumor.
- Tumor response in injected/uninjected lesion(s)
  - The subject-level injected and uninjected responses will be based on the tumor burden of only injected index lesions including injected new measurable lesions, or the tumor burden of only uninjected index lesions including uninjected new measurable lesions, respectively.
  - The lesion-level injected and uninjected response will evaluate the change of the area of each individual lesion.
- Similar to tumor response in injected/uninjected lesions, lesion-level and subject-level response may also be conducted for lesion subtypes, eg, cutaneous / subcutaneous, nodal.

For the subject-level tumor response by tumor burden type (injected, uninjected lesions), a response is achieved if the percentage of the specific tumor burden type reduction from baseline for both baseline and new measurable lesions (if applicable) is at least 50%. Overall tumor burden is calculated at a visit as the sum of tumor areas of all lesions of the same type. The incidence of subject-level tumor response will be reported as the proportion of subjects with an evaluable tumor burden of the corresponding type that achieves a response.

The incidence of lesion-level response will be reported as the proportion of evaluable lesions in response. A lesion is in response if the decrease in tumor area is  $\geq 50\%$ .

All overall tumor burden and lesion response analyses will be based on bi-dimensional lesion measurements reported at a tumor assessment and will not consider injected lesion longest diameters reported at the time of investigational product administration forms.

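### SAP Section 6 treats a missing pre-dose lesion area as absence, so a lesion already listed at baseline can be relabelled new and distort the Arm 1 injected and uninjected response

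*SAP*

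**What the plan says.** SAP Section 6 flags as baseline "Lesions measured at the most recent visit on or before receiving the first administration of talimogene laherparepvec", and requires a positive area. A lesion entered on the baseline measurable-lesion page with a "tumor area of zero or missing value at the last measurement on or before study day 1 will not be considered baseline lesions".

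The New Lesion entry has two limbs. One covers lesions that first appear after study day 1. The other covers "lesions without a positive lesion area in the last assessment on or before study day 1" that show a positive area at follow-up. For the lesion-level analysis, "Baseline tumor area of a new lesion is obtained from the earliest date with positive bi-dimensional tumor measurements after study day 1".

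Three entries define burden:

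- Baseline Tumor Burden (SAP Section 6): "The baseline tumor burden for a subject is the sum of the initial area of baseline lesions of the specific lesion type".
- Tumor Burden at a visit (SAP Section 6): also a sum over baseline lesions only.
- SAP 4.1.2.1.1, to which the Response entry in Section 6 refers: a subject responds when the "reduction from baseline for both baseline and new measurable lesions (if applicable) is at least 50" percent, and the burden at a visit is summed over every lesion of the type. Protocol 10.1.1.2 and Appendix D also bring new measurable lesions into the follow-up burden.

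**The concern.** A missing measurement is not evidence that a lesion was absent. Section 6 puts the two in one class, and the second limb of the New Lesion entry then turns a lesion already known at baseline into a new one. Under the response rule in SAP 4.1.2.1.1, that lesion counts in the numerator of the burden ratio and not in the denominator.

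Response in injected and uninjected lesions is a named secondary objective, reported in Arm 1 only. If the rule bites, a gap in the baseline record can decide whether a subject is a responder, whatever the tumor did. The SAP also holds two follow-up burden definitions, so the answer depends on which one is programmed.

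**Working it through.** The plan gives no figure on this point, so there is none to reproduce. The 50% threshold and the burden definitions come from SAP 4.1.2.1.1 and Section 6. The assessment schedule comes from Protocol Table 2 and Section 7.2.2. Lesion areas, lesion counts and responder counts below are assumptions for illustration.

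**Subject level under SAP 4.1.2.1.1.** Let B be the true baseline burden of one type, m the share of B held by the lesion without a usable pre-dose area, and s the true shrinkage, taken as equal for all lesions.

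- Recorded baseline burden = (1 − m)B
- Follow-up burden = (1 − s)B
- Scored reduction = 1 − (1 − s)/(1 − m)
- Scored as a response only if (1 − s) ≤ 0.5(1 − m), that is m ≤ 2s − 1

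A true responder (s ≥ 0.5) is therefore missed when m > 2s − 1:

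| True shrinkage s | Missed if m exceeds |
|---|---|
| 50% | 0% |
| 60% | 20% |
| 70% | 40% |
| 80% | 60% |
| 100% | never |

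With k equal lesions, m = 1/k. The shrinkage needed is then (1 + 1/k)/2, which is 75%, 67% and 62.5% for k = 2, 3 and 4. A true 60% is scored as 1 − 0.4/(1 − 1/k), which is 20%, 40% and 47%. If the lesion is the only one of its type, baseline burden is zero and the percentage is undefined.

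**Both definitions on the same data.** Take two injected lesions of 400 mm² each, the second without a usable pre-dose area.

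| Follow-up areas (mm²) | True reduction | SAP 4.1.2.1.1 | SAP 6 Tumor Burden |
|---|---|---|---|
| 160 and 160 | 1 − 320/800 = 60% | 1 − 320/400 = 20% | 1 − 160/400 = 60% |
| 160 and 400 | 1 − 560/800 = 30% | 1 − 560/400 = −40% | 1 − 160/400 = 60% |

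In the first row, SAP 4.1.2.1.1 loses a true responder. In the second, the Tumor Burden entry creates a false one.

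**Safeguards.** The Evaluable Tumor Burden entry checks only lesions that were already in the baseline burden, so the relabelled lesion does not trigger it. SAP 9.3.1 sends missing efficacy data to Section 4, which has no rule for a missing baseline area.

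**Lesion level.** The evaluability rule reads: "A baseline or new measurable lesion is defined as evaluable if it has an initial positive area followed by at least 1 assessment"; the later value must actually have been recorded. The relabelled lesion takes its first positive area after study day 1 as its baseline. Only one tumor assessment is scheduled between first dose and surgery (week 12, or shortly before an early surgery). The lesion usually has no second value and drops out as non-evaluable.

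**Effect on a rate.** Assume 75 evaluable Arm 1 subjects and 15 true responders, with exact 80% limits:

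- none lost: 15/75 = 20.0% (14.1 to 27.2)
- one lost: 14/75 = 18.7% (12.9 to 25.7)
- three lost: 12/75 = 16.0% (10.7 to 22.8)

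Each misclassified subject moves the rate by 1/75 = 1.3 points, and by more if fewer subjects have an evaluable burden of that type.

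**The case against.** The best defence is that the case is narrow. Lesions on the measurable page should have two recorded dimensions, and Appendix D requires the index-lesion sum to be calculated at baseline, so a listed lesion without an area should be uncommon. The Tumor Burden entry keeps a relabelled lesion out of both sums, and in the first example above that gives the correct 60%. The endpoints are descriptive. Most of this stands as a limit on size. It does not rescue the rule, because the Tumor Burden entry contradicts SAP 4.1.2.1.1 and fails in the second example.

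A reader might infer more than the documents support:

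- *That a true responder is always lost.* The loss is conditional on m > 2s − 1, and it arises under only one of the two burden definitions.
- *That a node imaged on one screening day is relabelled because calipers were used on a later day.* Appendix D says "All baseline evaluations should be performed as close as possible to randomization and never more than 4 weeks (ie, 28 days) prior to randomization", which does not require a single day. But Section 6 speaks of a visit, Table 2 puts imaging and clinical measurement in one screening column, and the general Baseline entry takes the latest value before dosing. A date-based reading is possible but not compelled.
- *That the baseline tumor count and sum of products are also wrong.* SAP 4.2 and 10.4 do not say they use this flag. The flag is keyed to the first talimogene laherparepvec dose, while those variables are not restricted to Arm 1.
- *That a given number of subjects is affected.* The documents give no basis for one.

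**Conclusion.** The point holds in a limited form. A lesion listed at baseline with no recorded pre-dose area is relabelled new once it has a positive area, however the visit wording is read. Under SAP 4.1.2.1.1 a true responder can then be scored a non-responder. Under the Tumor Burden entry in Section 6 a non-responder can be scored a responder. At lesion level the lesion is usually lost.

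Only the Arm 1 subject-level and lesion-level injected and uninjected responses are affected. Investigator-assessed overall response, RFS, R0 and pCR do not use this flag. The size per subject can be large (60% scored as 20%, or 30% as 60%), but the frequency is unknown. The formula assumes equal shrinkage across lesions. For a lesion never measured before dosing, m cannot be recovered from the data, so the error could not be corrected afterwards. This is a modest defect in a descriptive secondary analysis, worth correcting because the correction is cheap.

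**What to change.** Amend SAP Section 6 and 4.1.2.1.1 as follows:

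1. Define each lesion's baseline area as its latest non-missing bi-dimensional area on or before study day 1, within the screening window.
2. Let a lesion become new only if it was not listed at baseline or was recorded there as zero.
3. Class a listed lesion with no pre-dose area as baseline, not evaluable, and make that subject's burden of that type non-evaluable, or report the response both ways as a sensitivity analysis. Simply dropping the lesion from both sums is not enough, as the true 30% scored as 60% shows.
4. Reconcile the follow-up burden in SAP 4.1.2.1.1 with the Tumor Burden entry in Section 6, and state whether new measurable lesions are included.

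The cost is a few sentences and a programming rule, with no new data. A few subjects may become non-evaluable for injected or uninjected burden.

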The recommended volume of talimogene laherparepvec to be injected into the tumor(s) is dependent on the size of the tumor(s) and should be determined according to the injection volume guideline in [Table 1](#). The tumor size assessment for the injection should be done by clinical exam using a ruler or caliper for cutaneous lesions and palpable and protruding subcutaneous and nodal lesions, or by measurements under ultrasound of deep-seated subcutaneous and nodal lesions.

Table 1. Talimogene Laherparepvec Injection Volume Guideline Based on Tumor Size

Tumor Size (longest dimension)	Maximum Injection Volume
> 5.0 cm	4.0 mL
> 2.5 cm to 5.0 cm	2.0 mL
> 1.5 cm to 2.5 cm	1.0 mL
> 0.5 cm to 1.5 cm	0.5 mL
\leq 0.5 cm	0.1 mL

All reasonably injectable lesions (cutaneous, subcutaneous, and nodal disease that can be injected with or without ultrasound guidance) should be injected with the maximum dosing volume available on an individual dosing occasion (Table 1). On each treatment day, prioritization of injections is recommended as follows:

- any new injectable tumor that has appeared since the last injection
- by tumor size, beginning with the largest tumor
- any previously uninjectable tumor(s) that is now injectable

It is recommended that each lesion should receive the maximum amount possible to inject due to tumor properties at each visit before moving on to the next lesion, using the prioritization model above and the injection volume guideline based on tumor size per Table 1. Lesions should be injected until the maximum volume per day (4.0 mL) has been reached or there are no further injectable lesions, whichever comes first.

A subject will be treated with talimogene laherparepvec until week 12, all injectable tumors have disappeared, or intolerance of study treatment, whichever occurs first. Due to the mechanism of action, subjects may experience transient growth in existing tumors or the appearance of new tumors prior to maximal clinical benefit of talimogene laherparepvec. Therefore, subjects will be allowed to remain on talimogene laherparepvec treatment until week 12 of therapy unless, in the opinion of the investigator, immediate surgical resection or any other treatment for melanoma is warranted. If talimogene laherparepvec treatment will end prior to week 12, the investigator or designee should notify the sponsor's medical monitor as soon as possible.

The dose, start date, and lot number of talimogene laherparepvec are to be recorded on the CRF.

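### Lesions are called uninjected only if never injected, while the dosing order favours lesions that fail to shrink, so the uninjected-lesion response is likely overstated by an amount the documents do not fix

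*SAP*

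**What the plan says.** SAP Section 6 defines lesion type by the whole treatment period: "Baseline or new lesions that are reported as injected with talimogene laherparepvec at any time during the treatment period are considered injected lesions". The complement is: "Baseline or new lesions that are not reported as injected with talimogene laherparepvec are considered uninjected lesions".

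SAP Section 4.1.2.1.1 applies these groups: "The lesion-level injected and uninjected response will evaluate the change of the area of each individual lesion". A lesion responds if its area falls by at least 50%. The lesion-level rate is taken over evaluable lesions. The subject-level rate is taken over subjects with an evaluable burden of the given type. Diameters recorded on the dosing forms are not used.

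Protocol 6.2.1.1 governs which lesions are injected. "On each treatment day, prioritization of injections is recommended as follows": first "any new injectable tumor that has appeared since the last injection", then "by tumor size, beginning with the largest tumor", then "any previously uninjectable tumor(s) that is now injectable". It continues: "Lesions should be injected until the maximum volume per day (4.0 mL) has been reached or there are no further injectable lesions". There are six dosing days (weeks 1, 4, 6, 8, 10 and 12). Protocol 7.2.2 schedules one on-treatment tumor measurement, around week 12 or shortly before surgery if treatment ends early.

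For tumor response, the only sensitivity analysis in SAP Table 2 is a possible repeat in the efficacy analysis set.

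**The concern.** Group membership is decided during treatment by a rule that looks at lesion size. A lesion passed over at dose 1 that grows moves up the size ranking or may become injectable. One that shrinks moves down, and one that disappears cannot be injected. A single later injection moves the lesion out of the uninjected group for the whole analysis. Its lack of response before that injection is not captured either, because tumor measurement is scheduled only near week 12 and dosing-visit sizes are excluded. At subject level, someone whose only uninjected lesion is injected later drops out of the uninjected denominator.

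Response in uninjected lesions is a named secondary objective and endpoint. Readers will take it as evidence of an effect beyond the injection site, so a rate raised by selective loss of failures would overstate that evidence.

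**Working it through.** The plan gives no expected rate, precision or power for this endpoint, so there is no stated figure to reproduce.

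**Inputs**
- p: true response rate of lesions not injected at dose 1. Not in the documents. For illustration, 0.34 = 22% CR + 12% PR in non-injected non-visceral lesions of the earlier phase 3 study (Protocol 2.2); 0.20 is an assumption.
- q and r: shares of initially uninjected non-responders and responders, respectively, that are injected later. Neither is in the documents, so both are assumed.

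**Step 1, formula.** Under the ever/never rule the lesions still counted as uninjected are p(1-r) responders and (1-p)(1-q) non-responders:

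observed rate = p(1-r) / [p(1-r) + (1-p)(1-q)].

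This exceeds p only if 1-r > 1-q, that is, only if q > r.

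**Step 2, numbers**

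| p | q | r | p(1-r) | (1-p)(1-q) | observed |
|---|---|---|---|---|---|
| 0.34 | 0.50 | 0 | 0.340 | 0.330 | 0.340/0.670 = 0.51 |
| 0.34 | 0.50 | 0.25 | 0.255 | 0.330 | 0.255/0.585 = 0.44 |
| 0.34 | 0.50 | 0.50 | 0.170 | 0.330 | 0.170/0.500 = 0.34 |
| 0.34 | 0.25 | 0.50 | 0.170 | 0.495 | 0.170/0.665 = 0.26 |
| 0.20 | 0.50 | 0 | 0.200 | 0.400 | 0.200/0.600 = 0.33 |
| 0.20 | 0.50 | 0.25 | 0.150 | 0.400 | 0.150/0.550 = 0.27 |

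**Step 3, does the dosing order make q > r?** A simulation used the protocol's volume table, the 4.0 mL limit, six dosing days and largest-first ranking renewed at each visit. Lesion counts (3, 5 or 8 per subject), sizes, growth and injectability were assumed, and new tumors were not simulated. Of initially uninjected lesions, 70-83% of non-responders were later injected, against 27-59% of responders. The never-injected response was 0.20-0.22 where the true rate was about 0.10, 0.35-0.38 where it was 0.20, and 0.52-0.57 where it was 0.33-0.35. The rise was about 10 to 23 percentage points. When lesions were picked at random and growth could not make a lesion injectable, the rates were 0.10, 0.20-0.21 and 0.35, so the bias disappeared. This supports the direction; it does not estimate the size in this trial.

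**Step 4, a bound from below.** If status is fixed at dose 1 and every later-injected lesion counts as a non-response, the rate is p(1-r), which cannot exceed p. At p = 0.34, q = 0.50 and r = 0.25 it is 0.34 × 0.75 = 0.26. The ever/never figure is 0.44, so the two enclose 0.34. They enclose p whenever q is at least r.

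**The case against.** **The ever-injected rule has a purpose.** It keeps direct injection effects out of the uninjected group. That stands, and it is why the rule should be kept and supplemented. A reader might infer that the definition should be replaced by first-dose status. The documents do not support that: scoring every later-injected lesion as a failure gives p(1-r), which is biased downward. At p = 0.34 and the simulated r of 0.27 to 0.59 it is 0.34 × 0.73 = 0.25 down to 0.34 × 0.41 = 0.14.

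**Responders can be injected later too.** A response needs only a 50% fall in area, so a partial responder can remain injectable. Larger lesions that shrink free volume for smaller ones. A reader might take the r = 0 rows as the expected size, but nothing in the protocol implies r = 0.

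**The dosing order is softer than it looks.** It is a recommendation and does not name growth; growth acts through size rank and new injectability, and the latter ranks last. New lesions contribute little at lesion level, because an evaluable one needs a second measurement and on-treatment measurement is scheduled only near week 12.

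**Few lesions may switch.** By Protocol Table 1, 4.0 mL covers eight lesions of up to 1.5 cm (8 × 0.5 mL) or four of up to 2.5 cm (4 × 1.0 mL). If most lesions are injected at dose 1, little movement is possible. The documents give no lesion counts for this trial, so this cannot be settled. The 34% also comes from unresectable disease treated for longer.

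**Late first injection is not automatic failure.** A reader might infer that a lesion first injected at week 12 counts as an injected non-responder. It is scored by its area change. If it had already halved, it becomes an injected responder, and its departure lowers the uninjected rate.

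**The rationale does not rest on this endpoint.** A reader might link it to the systemic effect in Protocol 2.3. That section refers to R0 resection and to distant metastasis through micrometastatic disease; DMFS, a randomized comparison, addresses the latter.

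**Conclusion.** The point holds as a likely upward bias in the lesion-level uninjected response. It rests on one condition: that initially uninjected lesions which fail to respond are injected later more often than those which respond (q > r). The recommended order makes this likely without guaranteeing it. The subject-level rate can be affected through its denominator, but no size was calculated for it.

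The size is not determinable from the documents. At p = 0.34 and q = 0.50 the reported rate runs from 0.34 (r = 0.50) to 0.51 (r = 0). No planned analysis would show where the trial lies in that range.

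The consequence is limited. The endpoint is secondary, descriptive and confined to Arm 1. RFS, overall modified WHO response, R0 rate and pCR do not use this classification, and no inference about them follows. This is an inexpensive improvement to the plan.

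**What to change.** Keep the ever/never-injected analysis. Add to SAP Section 4.1.2.1.1 and Table 2 a prespecified sensitivity analysis, at lesion and subject level, that:

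- fixes lesion status at the first dose, or for a new lesion at the first dosing visit after it appears;
- keeps every lesion uninjected at that visit in the uninjected denominator;
- counts any such lesion injected before the response assessment as an uninjected non-response. At subject level the SAP should state the matching rule; counting the subject as a non-responder if any such lesion was injected before the assessment keeps the result a lower bound.

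Present the result beside the ever/never figure and label it a conservative lower bound. Report how many initially uninjected lesions were later injected, with their size at first injection.

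No dosing rule changes and no new data are needed: the SAP's own definition depends on per-lesion injection reports, and diameters of injected lesions are recorded at dosing visits. The cost is SAP wording and a little programming. The downside is that the added figure is biased downward when responding lesions are later injected, so it should not be read as the estimate itself.
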